## 11.2.4 Mean bisacodyl dose per week

Bisacodyl doses will be recorded for each patient in the eCRF. The mean bisacodyl dose per week (mg) will be calculated as

(sum of bisacodyl doses (mg) during the period of interest/number of days in the period of interest) x 7.

The mean bisacodyl dose per week (mg) will be assessed for the following time intervals: enrollment to Week 4 and Week 4 to Week 12.

## 11.2.5 Modified Himmelsbach Scale

The scores for each of 8 signs are summed to give a composite score ranging from 0 to 24 for each visit, where higher values indicate greater severity of symptoms. If more than 25% of the 8 signs are missing at a visit, the composite score will be set to missing. Changes from baseline to Week 12 in the modified Himmelsbach scale will be calculated as the post-baseline value minus the baseline value. Negative changes from baseline indicate improvement.

The primary baseline modified Himmelsbach values will be defined as the latest non-missing value collected prior to the first dose of study drug in the previous pivotal study (D3820C00004) (screening, Visit 1 or Week 0, Visit 3), and supportive baseline modified Himmelsbach values will be defined as the data collected at Visit 8 from the previous study D3820C00004 (also defined as Visit 1 of this study).

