#### 6.3.1 Safety variables

Safety variables include:

- Incidence, nature, and intensity of AEs, treatment-related AEs, SAEs, AEs leading to discontinuation, and specific safety areas of interest.
- Mean daily opioid dose for Weeks 4 and 12.
- Mean bisacodyl dose per week for Weeks 4 and 12.
- Change from baseline in the mean NRS pain score for Weeks 4, 8, and 12.
- Observed values and change from baseline in composite score in modified Himmelsbach scale for the evaluation of centrally mediated opioid withdrawal symptoms at Week 12.
- Changes in vital signs and physical examination.

- Changes in laboratory assessments (ie, chemistry, hematology, and U/A).
- Changes in ECGs.

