### 6.3.9 Modified Himmelsbach Scale

Patients are rated by examination for symptoms of opioid withdrawal using the modified Himmelsbach scale. The modified Himmelsbach scale will be administered by a clinician at the study site. Patients will be rated with respect to the following symptoms as observed at the time of the assessment: yawning, lacrimation, rhinorrhea, perspiration, tremor, mydriasis, piloerection, and restlessness. The signs will be quantified on a scale of 0 to 3, with 0=none, 1=mild, 2=moderate, 3=severe. (Himmelsbach 1941; Culpepper-Morgan et al 1992, Webster et al 2008). To ensure adequate inter-rater agreement, raters will undergo training on proper scoring using the modified Himmelsbach scale and will receive certification provided by Bracket Global. The modified Himmelsbach scale will be administered at Visit 1 (enrollment - data obtained at the Visit 8 of previous study D3820C00004) and Visit 4 (Week 12). Changes in this scale should generally not be reported as AEs unless standard criteria for AE reporting are otherwise met.

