# 11. EVALUATION AND CALCULATION OF VARIABLES

## **11.1** Calculation or derivation of efficacy variable(s)

## 11.1.1 PAC-SYM

For the PAC-SYM, each item is scored as 0=absence of symptom, 1=mild, 2=moderate, 3=severe, and 4=very severe. The 12 items of the PAC-SYM are assigned to 3 domains:

- Abdominal symptoms (items 1 to 4)
- Rectal symptoms (items 5 to 7)
- Stool symptoms (items 8 to 12).

Each domain score will be calculated as the mean of the non-missing items for that domain. The total score will be calculated as the mean of all non-missing items. If more than 50% of values for a domain or the total score are missing for a visit, the values for that score will be set to missing.

Change from baseline in the PAC-SYM domain and total scores will be calculated for Weeks 4, 12, and 14 as the post-baseline value minus the baseline value. Negative changes from baseline indicate improvement.

The primary baseline PAC-SYM values will be defined as the latest non-missing value collected prior to the first dose of study drug in the previous pivotal study (D3820C00004) (screening, Visit 1 or Week 0, Visit 3), and supportive baseline PAC-SYM values will be defined as the data collected at Visit 8 from the previous study D3820C00004 (also defined as Visit 1 of this study).

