## 11.1.2 **PAC-QOL**

For the PAC-QOL, each of the 28 items is scored from 0 to 4. For items 18, 25, 26, 27, and 28, higher scores represent better outcomes. The scores for these items will be reversed (reversed score=4-original score), so that higher scores represent worse outcomes for all items. The 28-item PAC-QOL is divided into 4 subscales:

• Physical discomfort (items 1 to 4)

- Psychosocial discomfort (items 5 to 12)
- Worries/concerns (items 13 to 23)
- Satisfaction (items 24 to 28).

For each visit, individual subscale scores will be calculated as the mean of the non-missing items for that subscale. The total score will be calculated as the mean of all non-missing items. If more than 50% of values for a subscale score or the total score are missing for a visit, the values for that score will be set to missing.

Change from baseline in the PAC-QOL subscale and total scores will be calculated for Weeks 4, 12, and 14 as the post-baseline value minus the baseline value. Negative changes from baseline indicate improvement.

The primary baseline PAC-QOL values will be defined as the latest non-missing value collected prior to the first dose of study drug in the previous pivotal study (D3820C00004) (screening, Visit 1 or Week 0, Visit 3), and supportive baseline PAC-QOL values will be defined as the data collected at Visit 8 from the previous study D3820C00004 (also defined as Visit 1 of this study).

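### The modified Himmelsbach composite is an unscaled sum that is kept with one or two signs missing, so those visits are scored on a shorter scale

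*Protocol*

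**What the plan says.** Protocol Section 6.3.9 lists eight signs for the clinician to rate and gives the grading: "The signs will be quantified on a scale of 0 to 3, with 0=none, 1=mild, 2=moderate, 3=severe". Section 11.2.5 builds the composite from them: "The scores for each of 8 signs are summed to give a composite score ranging from 0 to 24 for each visit". The next sentence but one concerns missing data: "If more than 25% of the 8 signs are missing at a visit, the composite score will be set to missing". Nothing is said about how the score is formed when some signs are missing but the limit is not exceeded.

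For change, the section states: "Changes from baseline to Week 12 in the modified Himmelsbach scale will be calculated as the post-baseline value minus the baseline value". It adds: "Negative changes from baseline indicate improvement".

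The two constipation questionnaires also tolerate missing items, but they are scored differently. For PAC-SYM (Section 11.1.1): "Each domain score will be calculated as the mean of the non-missing items for that domain". For PAC-QOL (Section 11.1.2): "individual subscale scores will be calculated as the mean of the non-missing items for that subscale".

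Section 6.3.1 lists the composite among the safety variables: "Observed values and change from baseline in composite score in modified Himmelsbach scale for the evaluation of centrally mediated opioid withdrawal symptoms at Week 12".

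**The concern.** A tolerance for missing items is harmless when the score is a mean, because the divisor shrinks with the number of items. It is not harmless when the score is a sum. A sign that was not rated then adds nothing, exactly as a sign rated absent adds nothing. Scores from incomplete visits would be summarised with complete ones as though all were on the 0 to 24 scale.

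The variable is of some importance here. The primary objective is safety and tolerability, opioid withdrawal is one of the listed safety areas of interest (Section 6.3.15), and this is the only withdrawal rating scale in the study. The only new rating in this study is at Visit 4 (Week 12, or early termination); the Visit 1 value is carried over from Visit 8 of the previous study (Section 6.3.9). Section 12.2 also plans an outlier analysis that includes this scale. A partial sum could leave a patient who has withdrawal signs below whatever cut-off is chosen.

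**Working it through.** **Inputs.** Eight signs, each 0 to 3 with 0 for none (Section 6.3.9). Composite = sum; set to missing only if more than 25% of signs are missing; change = Week 12 minus baseline, with negative read as improvement (Section 11.2.5).

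**Step 1: reproduce the stated range.** Minimum 8 × 0 = 0; maximum 8 × 3 = 24. This agrees with the protocol, but only when all eight signs are rated.

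**Step 2: what the tolerance admits.** The maximum sum with m signs missing is 3 × (8 − m).

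| Signs missing (m) | Share missing | Composite | Maximum sum |
|---|---|---|---|
| 0 | 0% | kept | 24 |
| 1 | 12.5% | kept | 21 |
| 2 | 25% (not more than 25%) | kept | 18 |
| 3 | 37.5% | set to missing | – |

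**Step 3: shortfall in the observed composite.** The shortfall is the sum of the true scores of the missing signs. Each lies between 0 and 3, so the shortfall is 0 to 3 points for m = 1 and 0 to 6 points for m = 2. It is zero when the missing signs were truly absent, and it is never negative.

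**Step 4: shortfall if severity is equal across signs (an assumption).** If every sign has grade s, the true composite is 8s, the raw sum is s(8 − m), and the relative shortfall is m/8.

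| Grade of every sign | True composite | Raw sum, 1 missing | Raw sum, 2 missing |
|---|---|---|---|
| mild (1) | 8 | 7 | 6 |
| moderate (2) | 16 | 14 | 12 |
| severe (3) | 24 | 21 | 18 |
| shortfall | – | 12.5% | 25% |

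**Step 5: change from baseline.** Take a patient with every sign mild at both visits, so the true change is 0. With mB signs missing at baseline and mW at Week 12, the raw change is (8 − mW) − (8 − mB) = mB − mW.

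| Missing at baseline | Missing at Week 12 | Raw change | Reads as |
|---|---|---|---|
| 0 | 2 | −2 | improvement |
| 2 | 0 | +2 | worsening |
| 2 | 2 | 0 | no change |

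**Step 6: test the proposed rule.** Prorated composite = (sum of rated signs ÷ number rated) × 8. In every row of Step 4 it returns 8, 16 or 24, and in Step 5 it returns a change of 0. It is not exact when the missing signs differ from the rated ones:

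- Two missing signs truly absent and the other six mild: true 6, raw 6, prorated 6 ÷ 6 × 8 = 8, so proration is 2 too high.
- Only the two missing signs present, both severe: true 6, raw 0, prorated 0, so proration does not help.

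**The case against.** The strongest reply is that Section 11.2.5 never says that a missing sign counts as zero. It gives a limit for missing signs and is silent on scoring below that limit. A limit of this kind is compatible with proration, the stated 0 to 24 range fits a partial sum poorly, and Section 12.2 promises a full SAP before unblinding that could supply the rule. This stands in part: scoring an unrated sign as zero is the arithmetic result of following the text, not a stated intention. It does not remove the point. The protocol itself fixes both the sum and the tolerance, and where it wanted averaging over available items, for PAC-SYM and PAC-QOL, it said so.

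A reader might infer that the error always runs towards improvement and so systematically hides withdrawal. The documents do not support that. The limit applies at any visit, so the baseline score is affected too, and Step 5 shows a false worsening as readily as a false improvement. Only the observed composite at a given visit errs in one direction. Nor do the documents support 25% as an average loss; that figure rests on equal severity across signs.

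Several points on size also stand. Raters are trained and certified (Section 6.3.9), and missing data are queried (Section 10.2), so missing signs may be uncommon. Patients with apparent withdrawal signs at enrollment are excluded (exclusion criterion 7), which suggests low scores, though it does not guarantee them at Week 12. No statistical test is planned, and no decision rule in the protocol uses the composite. Adverse events suggestive of withdrawal are summarised separately (Section 12.2.1). The study is double-blind, and nothing indicates that missing signs would differ by arm.

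**Conclusion.** The point holds in a limited form. Followed literally, Section 11.2.5 gives a composite on a 0 to 21 or 0 to 18 scale when one or two signs are missing, and mixes it with scores on the 0 to 24 scale. The observed composite at such a visit is too low by 0 to 3 or 0 to 6 points, or by 12.5% or 25% under the assumption of equal severity. The direction of the error in the change score depends on which visit has more missing signs.

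How much this moves the group summaries cannot be computed, because the protocol gives neither a rate of missing signs nor item-level scores. Given trained raters and data queries, the effect is probably small. It is a scoring rule to correct, and it does not threaten the study's conclusions. An SAP that states a rescaling rule would settle it in practice, but the protocol text would still need to agree.

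**What to change.** Add to Section 11.2.5: when one or two of the eight signs are missing, the composite is 8 times the mean of the rated signs; when more than two are missing, it is set to missing; the rule applies to the primary baseline, the supportive baseline and Week 12. This keeps the 0 to 24 range, leaves the existing limit unchanged, and is consistent with the scoring of PAC-SYM and PAC-QOL.

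The cost is one sentence and no change to data collection, and it can be settled before unblinding. The statistical price is the assumption that missing signs resemble the rated ones, which is open to question for signs as unlike as mydriasis and restlessness; Step 6 shows the error when it fails. Requiring all eight signs would avoid that assumption, at the price of losing the composite at any visit with a missing sign. Reporting the number of composites based on six or seven signs, by visit and treatment group, would show whether the choice matters.

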## 11.2.6 Laboratory safety assessments

Changes from baseline to each visit for all patients who have a baseline laboratory test and the corresponding post-baseline laboratory test (Weeks 12 and 14) will be calculated as the post-baseline test value minus the baseline test value.

The primary baseline laboratory values will be defined as the latest non-missing value collected prior to the first dose of study drug in the previous pivotal study (D3820C00004) (screening, Visit 1 or Week 0, Visit 3), and supportive baseline laboratory values will be

defined as the data collected at Visit 8 from the previous study D3820C00004 (also defined as Visit 1 of this study).

Laboratory test results will also be compared with the laboratory reference ranges, and values that are outside the applicable reference range will be flagged as high (H) or low (L). In addition, markedly abnormal values or changes from baseline will be identified.

## 11.2.7 Physical examination

Observed results and change from baseline to Week 12 for physical examination will be reported.

The primary baseline physical examination results will be defined as the latest non-missing value collected prior to the first dose of study drug in the previous pivotal study (D3820C00004) (screening, Visit 1 or Week 0, Visit 3), and supportive baseline physical examination results will be defined as the data collected at Visit 8 from the previous study D3820C00004 (also defined as Visit 1 of this study).

## 11.2.8 Weight

Change from baseline to Week 12 for weight will be calculated as the visit assessment minus the baseline value. Markedly abnormal values or changes from baseline will be identified.

The primary baseline weight value will be defined as the latest non-missing value collected prior to the first dose of study drug in the previous pivotal study (D3820C00004) (screening, Visit 1 or Week 0, Visit 3), and supportive baseline weight value will be defined as the data collected at Visit 8 from the previous study D3820C00004 (also defined as Visit 1 of this study).

## **11.2.9** Body temperature and respiratory rate

Change from baseline to Week 12 for body temperature and respiratory rate will be calculated as the post-baseline test value minus the baseline test value. Markedly abnormal values or changes from baseline will be identified.

The primary baseline body temperature and respiratory rate values will be defined as the latest non-missing value collected prior to the first dose of study drug in the previous pivotal study (D3820C00004) (screening, Visit 1 or Week 0, Visit 3), and supportive baseline body temperature and respiratory rate values will be defined as the data collected at Visit 8 from the previous study D3820C00004 (also defined as Visit 1 of this study).

## 11.2.10 ECG

Changes from baseline to each post-baseline visit (Weeks 12 and 14) for ECG interval data and rate data will be derived by subtracting the baseline value from the final assessment value, where baseline. Markedly abnormal values or changes from baseline will be identified.

The primary baseline ECG values will be defined as the latest non-missing value collected prior to the first dose of study drug in the previous pivotal study (D3820C00004) (screening, Visit 1 or Week 0, Visit 3), and supportive baseline ECG values will be defined as the data collected at Visit 8 from the previous study D3820C00004 (also defined as Visit 1 of this study).

## 11.2.11 Vital signs

Changes from baseline in vital signs (sitting blood pressure and pulse) at each post-baseline visit (Weeks 4, 8, 12, and 14) will be derived as the value at the visit minus the baseline value for the same assessment. Markedly abnormal values or changes from baseline will be identified.

The primary baseline vital sign values will be defined as the latest non-missing value collected prior to the first dose of study drug in the previous pivotal study (D3820C00004) (screening, Visit 1 or Week 0, Visit 3), and supportive baseline vital sign values will be defined as the data collected at Visit 8 from the previous study D3820C00004 (also defined as Visit 1 of this study).

## 11.2.12 C-SSRS

Occurrence of suicidal behavior after baseline up to the final assessment (Week 14) will be defined as having answered "yes" to at least 1 of the 4 suicidal behavior sub-categories (actual attempt, interrupted attempt, aborted attempt, and preparatory acts or behavior) at any post-baseline evaluation.

Occurrence of suicidal ideation after baseline up to the final assessment (Week 14) will be defined as having answered "yes" to at least 1 of the 5 suicidal ideation sub-categories (wish to be dead, non-specific active suicidal thoughts, active suicidal ideation with any methods [not plan] without intent to act, active suicidal ideation with some intent to act [without specific plan], and active suicidal ideation with specific plan and intent) at any post-baseline evaluation.

The primary baseline C-SSRS values will be defined as the latest non-missing value collected prior to the first dose of study drug in the previous pivotal study (D3820C00004) (screening, Visit 1 or Week 0, Visit 3), and supportive baseline C-SSRS values will be defined as the data collected at Visit 8 from the previous study D3820C00004 (also defined as Visit 1 of this study).

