#### Other reporting guidance

It is important to distinguish between serious and severe AEs. Severity is a measure of intensity whereas seriousness is defined by the criteria in Section 6.3.3. An AE of severe intensity need not necessarily be considered serious. For example, nausea that persists for several hours may be considered severe nausea, but not an SAE. On the other hand, a stroke that results in only a limited degree of disability may be considered a mild stroke, but would be an SAE.

If a diagnosis of the patient's condition has been made, then the diagnosis should be recorded as the SAE or the AE. In instances of well-recognized symptoms, they can be recorded as the commonly used diagnosis (eg, fever, runny nose, and cough can be recorded as "flu"). However, if a diagnosis of the patient's condition has not been made, or if the individual symptoms are not well recognized, then the individual symptoms should be recorded separately.

Should an overdose occur, it must be reported in accordance with the procedures described in Section 13.2. All overdoses, with or without associated symptoms, should be reported as AEs.

Suicide and attempted suicide, irrespective of the method, but occurring in connection with the use of study drug, should be reported as AEs (serious or nonserious). The event should be identified as suicide or attempted suicide, and the method of the suicide or attempt should be provided. If an attempted suicide meets the criteria for an SAE, the event must be reported according to the guidelines in Section 6.3.5. Suicidal thoughts and preparation for suicide should also be regarded as AEs. All events of suicidality will be monitored via the C-SSRS.

Pregnancy in itself is not regarded as an AE unless there is a suspicion that the IP has interfered with the effectiveness of a contraceptive medication. (To be eligible for this study, WOCBP and at risk of pregnancy must be using a reliable method of contraception; see Inclusion Criterion #6, Section 4.1). Should a pregnancy occur, it must be reported in accordance with the procedures described in Section 13.3.

In the clinical study report (CSR), the terms used by the investigator to record AEs will be mapped to preferred terms using a standard AE dictionary, Medical Dictionary for Regulatory Activities (MedDRA).

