#### 6.3.14 Other safety assessments

#### 6.3.14.1 C-SSRS

The C-SSRS is a unique, simple, and short method of assessing both behavior and ideation that tracks all suicidal events, and provides a summary of suicidality (Posner et al 2007). It assesses the lethality of attempts and other features of ideation (frequency, duration, controllability, reasons for ideation, and deterrents), all of which are significantly predictive of completed suicide.

The C-SSRS will be administered at all study visits by a trained rater. The trained rater will record the clinical observation on the scale, which will be used as the source document. If at all possible, the same individual should perform the assessment at each visit to reduce scoring variability. In the event the primary rater is not available, a designated back-up rater who meets the same qualifications may perform the C-SSRS.

If a patient indicates having a rating of type 4 or 5 suicidal ideation on the C-SSRS suicidal ideation scale at any time since the previous visit when the C-SSRS was administered or indicates having had any suicidal behavior since the previous visit, the patient should be referred to a mental health professional immediately. If the C-SSRS is administered by a rater other than the PI, it is recommended that the PI confirms suicidal ideation before making a referral to mental health services, however this should not delay the referral.

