All laboratory test results, vital signs (sitting blood pressure and pulse), ECG results, body temperature, respiratory rate, and weight will be summarized for each treatment group using descriptive statistics at each visit for observed values and change from baseline.

The overall incidence, as well as shifts from baseline to each post-baseline visit, of potentially clinically significant laboratory test results, vital signs, ECG results, body temperature, respiratory rate, and weight will be summarized by treatment group. For visits where triplicate ECGs are obtained, the mean value of the 3 measurements will be used in the analysis.

Physical examination results (normal/abnormal by body system) will be summarized for each visit by treatment group. Changes from baseline in the physical examination results will be assessed using shift tables.

The proportion of patients with suicidal behavior and suicidal ideation throughout the study based on the C-SSRS will be presented for each treatment group. The proportion of patients within each of the 4 suicidal behavior categories and within each of the 5 suicidal ideation sub-categories will also be presented for each treatment group. Descriptive statistics on the total number of attempts, total number of interrupted attempts, and total number of aborted attempts will be summarized for each treatment group.

Total exposure to NKTR-118 12.5 and 25 mg will be summarized combining the data from the current study with the exposure data from the previous pivotal study (D3820C00004).

Safety parameters may also be summarized by age group, gender, race, region, and response to laxatives (LIR, non-LIR), as appropriate.

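### The C-SSRS suicidal-behavior summary has no category for completed suicide, so a suicide with no earlier post-baseline endorsement is not counted in it

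*Protocol*

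**What the plan says.** Section 11.2.12 of the protocol classes a patient as having suicidal behavior if, at any evaluation after baseline and up to Week 14, the answer is positive for "at least 1 of the 4 suicidal behavior sub-categories (actual attempt, interrupted attempt, aborted attempt, and preparatory acts or behavior".

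Section 12.2.1 plans the by-arm proportion with suicidal behavior and with suicidal ideation over the whole study. It then breaks both down: "The proportion of patients within each of the 4 suicidal behavior categories and within each of the 5 suicidal ideation" sub-categories. It adds descriptive statistics for the "total number of attempts, total number of interrupted attempts, and total number of aborted attempts". Neither section mentions completed suicide.

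On administration, section 6.3.14.1 says: "The C-SSRS will be administered at all study visits by a trained rater". It continues: "The trained rater will record the clinical observation on the scale, which will be used as the source document".

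On scope, section 6.3.14.1 describes the instrument as one that "tracks all suicidal events, and provides a summary of suicidality". Section 6.3.4 (Other reporting guidance), in the paragraph on suicide and attempted suicide, ends: "All events of suicidality will be monitored via the C-SSRS".

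That same paragraph requires suicide in connection with study drug to be reported as an adverse event (AE) and identified as suicide. Section 6.3.4 also collects date and probable cause of death for serious adverse events (SAEs), and section 12.2.1 tabulates SAEs and AEs leading to death by treatment group.

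**The concern.** All four categories are rated at a visit, and a patient who has died attends none. Completed suicide is not a category, so the most severe form of suicidal behavior can reach the summary only if a lesser form was recorded earlier.

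The C-SSRS table is also the only by-arm suicidality summary that the protocol specifies. The AE groupings that section 12.2.1 names for separate summary are central opioid withdrawal, abuse potential and bowel perforation. Section 6.3.15 adds cardiovascular events. Its list is open-ended, but suicidality is not on it. No step links AE or SAE reports of suicide to the C-SSRS count.

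At stake is the ordering of the arms in that one table. The analysis is descriptive (section 12.2), so readers will compare raw counts. If events are few, an arm with one suicide could show no suicidal behavior beside an arm that shows one aborted attempt.

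**Working it through.** The protocol gives no figure to reproduce: the study has no formal sample size calculation and no statistical testing. The check is a reading of the rule, followed by an illustration of size.

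**Following one patient through the rule**

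1. *Timing.* Sections 3.1.2 to 3.1.3 place the C-SSRS at Days 29, 57, 85 and 99. The gaps are 57 − 29 = 28 days, 85 − 57 = 28 days and 99 − 85 = 14 days.
2. *A suicide between two visits.* No later scheduled visit or early termination visit takes place, and the protocol provides no rating after death.
3. *Numerator.* Section 11.2.12 needs a positive answer in one of four categories at a post-baseline evaluation. The patient qualifies only if (a) an item was endorsed at an earlier post-baseline visit, or (b) a rater coded the fatal act afterwards as an actual attempt. The protocol does not provide for (b). Without (a), the patient is not in the numerator.
4. *Denominator.* Section 12.1.1 assigns the safety analysis set to safety variables, and 11.2.12 stands under the safety derivations. That favours keeping the patient in the denominator. No C-SSRS-specific denominator is given, so exclusion as missing is also possible. The case is absent from the numerator either way.

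**Side by side**

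| Section | Content | Completed suicide covered? |
|---|---|---|
| 6.3.4 | All suicidality events monitored via the C-SSRS | Yes, as stated |
| 11.2.12 | Four categories rated at evaluations | No |
| 12.2.1, C-SSRS | Same four categories; three kinds of attempt counted | No |
| 12.2.1, AEs | SAEs and AEs leading to death by arm | Yes, as AE or death |

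**Size of one uncounted case**

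Inputs: up to 630 patients (section 3.1) in three treatment groups. Equal arms are an assumption, since the allocation ratio is not stated.

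- Equal split: 630 / 3 = 210 per arm; 1 / 210 = 0.48 percentage point.
- Assumed smaller enrolment of 100 per arm: 1 / 100 = 1.0 percentage point.

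**Illustration with 210 per arm:** arm A has one suicide with no earlier endorsement, and arm B has one aborted attempt.

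- As planned: arm A 0/210 = 0% (or 0/209 = 0% if dropped as missing); arm B 1/210 = 0.48%.
- With a fifth category: arm A 1/210 = 0.48%; arm B 1/210 = 0.48%.

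**The case against.** The strongest reply is that nothing is lost from the safety analysis. Death is an SAE criterion, every SAE must be reported, cause of death is collected, and a suicide would appear by arm in the AE, SAE and fatal-event tables. This stands, and it limits the point to one table. A reader might infer that the trial would fail to report a suicide; the documents do not support that.

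A reader might also infer that such a patient is tabulated as having no suicidal behavior. That goes too far. An earlier positive answer would count, and how a patient with no later C-SSRS is classed is not stated. What can be said is that the case is not counted as suicidal behavior.

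Nor are the categories simply self-reported: a trained rater administers the scale and records the observation. The protocol does not say whether a fatal act may be entered as an actual attempt, but it ties rating to visits, so this does not close the gap.

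It can further be said that the statement in section 6.3.14.1 describes the instrument in general, that the C-SSRS is absent from the safety-variable lists in the synopsis and section 6.3.1, and that denominators usually belong in the statistical analysis plan. The first weakens the conflict with that section but leaves the sentence in section 6.3.4. The second lowers the importance. The third is fair for the denominator, but the four-category rule is fixed in the protocol itself.

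**Conclusion.** The definition is wrong as written, with minor severity. Sections 11.2.12 and 12.2.1 fix a rule under which a suicide with no item endorsed at an earlier post-baseline visit cannot enter the suicidal-behavior count. That does not fit the sentence in section 6.3.4 or the whole-study proportion promised in section 12.2.1.

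The defect is confined to the by-arm C-SSRS summary. No test or decision rule depends on it. The effect, about 0.5 percentage point per case with 210 per arm and 1.0 point with 100, is hypothetical. It rests on assumed arm sizes and on such a case occurring; the protocol gives no expected event rate.

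**What to change.** In sections 11.2.12 and 12.2.1:

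- Add completed suicide as a fifth suicidal-behavior category, taken from the AE/SAE and death records, so that it does not depend on a visit rating.
- Define suicidal behavior as any of the five categories, and show the fifth as its own row in the by-arm table.
- State the safety analysis set as the denominator for the C-SSRS proportions.
- Add a step that reconciles AE and SAE reports of suicide and attempted suicide with the C-SSRS count.

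The data are already collected under section 6.3.4. The cost is a few lines of text and minor programming and reconciliation work. No visit or procedure changes.
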